TITLE	Effectiveness of nonspecific methods of treatment and Zopiclone for chronic insomnia
SPONSOR	
FUNDING ORGANIZATION	
NUMBER OF SITES	
RATIONALE	Importance of chronic insomnia (CI) problem is determined by its high prevalence rate, comorbidity and resistance to the treatment. There are pharmacological and cognitive-behavioral approaches to the CI treatment. Even after considering all the specific advantages and drawbacks of both methods of CI treatment a clinician would be still in question, which one would be preferable in a particular case.
STUDY DESIGN	Prospective randomized crossover study
PRIMARY OBJECTIVE	to test the effectiveness of short BBT-I program for chronic insomnia in comparison with zopiclone
SECONDARY OBJECTIVES	to find anthropometric, psychological and polysomnographic predictors of effectiveness of each method
NUMBER OF SUBJECTS	
SUBJECT SELECTION CRITERIA	
Inclusion Criteria: meeting the criteria for chronic insomnia according ICSD-3 willingness to take part in the study and signed informed consent form
 
Exclusion Criteria: (1) inability to stop taking medications that have a proven impact on sleep at least one week before and during the study; (2) history of alcohol or drug abuse; (3) major depressive disorder or other severe mental disorder identified by a clinical assessment and medical history; (4) dementia; (5) pregnancy or lactation; (6) shift or night work; (7) medical problems that would be a direct cause of sleep complaints: moderate/severe sleep apnea, defined as an apnea–hypopnea index of ≥ 15 events per hour, periodic limb movement disorder defined as a periodic leg movement index ≥ 15 events per hour or restless legs syndrome; (8) other serious chronic conditions or exacerbation of chronic disorder preventing further participation.

TEST PRODUCT, DOSE, AND ROUTE OF ADMINISTRATION	
2-week Brief behavioral therapy program includes a question-and-answer part; a didactic presentation of sleep regulation mechanisms; an examination of patient's sleep log; explanation of sleep restriction method and prescription of individual regimen of sleep; explanation of stimulus control method; sleep hygiene education; discussion of relaxation techniques, providing with relaxation audio recording.
 
BBT-I first group Will receive two-week brief behavioral therapy followed by medication therapy (zopiclone).

CONTROL GROUP OR OTHER STUDY ARMS (if applicable)	
Imovan (zopiclone) intake in a dose of 7,5 mg 30 minutes before bedtime for two weeks
 
zopiclone first group will get the medication therapy (zopiclone) for the first two weeks followed by brief behavioral therapy

DURATION OF SUBJECT PARTICIPATION AND DURATION OF STUDY	
Subjects will be on study for up to 8 weeks
 
Screening: every 2 weeks Treatment: 2 treatment courses 2 weeks each Follow-up: 2-week washout periods after each treatment course
 
The total duration of the study was 24 months

CONCOMITANT MEDICATIONS	
Prohibited: substances affecting sleep (hypnotics, antidepressants, anxiolytics, antihistamine)

EFFICACY EVALUATIONS	
Questionnaires (ISI, BDI, STAI, PSQI, DBAS, SHI, Big Five Questionnaire, TAS-20), Polysomnography, β-adrenoreactivity test

PRIMARY ENDPOINT	
 • ISI
SECONDARY ENDPOINTS	
 • BDI, STAI, PSQI, DBAS, SHI, β-adrenoreactivity test
OTHER EVALUATIONS	
Polysomnography, Big Five Questionnaire for evaluation of personal traits

SAFETY EVALUATIONS	
All subjects will be asked about well-being and possible adverse effects of treatment, on each biweekly visit. In the case of condition exclusionary for study participation (exacerbation of disease, starting medicines, incompatible with zopiclone etc.) when it is not in the subject's best interest to continue the subject may be discontinued from study

PLANNED INTERIM ANALYSES	
When approximately 50% of subjects have completed the study, an interim analysis will be conducted by the investigator. Serious adverse events will be monitored by the committee on an ongoing basis throughout the study.


STATISTICS Primary Analysis Plan
	
Analysis of insomnia treatment will be conducted only for patients matching inclusion and exclusion criteria who will complete at least one treatment course (BBT-I or medication) and fill in questionnaires prior and after the treatment. Continuous variables will be presented in means and standard deviation (M±SD). Categorical and rank variables will be presented as percentages.
 
Statistical significance of differences between group for continuous variables will be evaluated with Student’s t-test after confirmation of normal variable distribution by Kolmogorov-Smirnov test.
 
For continuous variables with distribution other than normal Mann-Whitney U-test will be used. For comparison of the proportions Pearson chi-squared test will be performed.
 
Criterion of response to the treatment is defined as the reduction of ISI score reduction of >7 points from baseline. Remission criterion is defined as final ISI score of 7 points or less. Nonresponse criterion is defined as ISI score decrease of ≤7 points from baseline. Based on these dichotomic values participants will be divided into two groups: responders and nonresponders for each method of treatment.
 
Comparison of responders and nonresponders baseline quantitative characteristics will be performed using Student’s t-test (for normal data distribution) or Mann-Whitney U-test (for abnormal data distribution). Statistical significance will be set at a p-value less 0,05.

Rationale for Number of Subjects
	
Study design allows to compare two therapeutic approaches with a relatively small sample size and to determine the predictors of effectiveness for each treatment. Thus 40 patients get 2 therapeutic approaches. This is the representative sample size enough to produce normal variable distribution for further parameter statistical analysis.

PURPOSE OF THE INVESTIGATION

Name of investigational method

Brief behavioral therapy program
Imovan (zopiclone)

Intended use of the investigational method

2-week Brief behavioral therapy will be performed in two 1 hour session for treatment of chronic insomnia (CI)

Imovan (zopiclone) in a dose of 7,5 mg has to be taken 30 minutes before bedtime for two weeks

Overview of Clinical Studies

The main treatment approaches for chronic insomnia with proven efficacy are pharmacologic and behavioral treatment. In accordance with the results of multiple clinical trials and meta-analyses both methods have comparable effectiveness in terms of sleep quality ranging between 64% (Buysse et.al., 2011) and 88% (Carson, McDonagh, Thakurta, and Yen P. 2008).

GABA(a) agonists being the most widely used hypnotics could cause residual daytime sedation and safety concerns like the risk of drug addiction, overdose and intoxication along with cognitive toxicity, falls and hip fractures especially in elderly persons (Pagel & Parnes, 2001)

The second approved treatment option for insomnia is cognitive-behavioral treatment of insomnia combining behavioral and psychological techniques. Unlike hypnotics this method has consistent long-term efficacy with few adverse effects (Morin et.al., 2016). On the other hand it requires special training of therapist, compliance of patient and noticeable time expenditures of both. Hence shortened and simplified behavioral approaches have been developed. It includes brief behavioral treatment for insomnia (BBT-I) lasting four weekly sessions instead of 6-8, online sessions, telephone consultations, and self-help approaches. Although there are not enough data for meta-analysis, BBT-I proved its efficacy in a number of clinical comparative studies (Bootzin, 2004).

STUDY RATIONALE

Even after considering all the specific advantages and drawbacks of pharmacological and cognitive-behavioral methods of CI treatment a clinician would be still in question, which one would be preferable in a particular case. There are still questions about the reason why CBT or pharmacotherapy or even their combination didn't reach 100% treatment response. So the treatment response predictors identification is required for individualized treatment

Risk / Benefit Assessment

Brief behavioral therapy has no potential adverse effects, risks of addiction or tolerance.

Zopiclone has possible hypersensitivity adverse effects as well as possible effects on central nervous system: taste disturbance; less commonly nausea, vomiting, dizziness, drowsiness, dry mouth, headache; rarely amnesia, confusion, depression, hallucinations, nightmares; very rarely light headedness, incoordination, paradoxical effects. Nevertheless it remains medication recommended for insomnia treatment in accordance with international guidelines

STUDY OBJECTIVES

Primary Objective

To test the effectiveness of short BBT-I program for chronic insomnia in comparison with zopiclone in Russian population.

Secondary Objectives

Identification of anthropometric, psychological and polysomnographic predictors of effectiveness of each method.

STUDY DESIGN

Study Overview

Prospective randomized crossover study. In accordance with this design every patient will receive two different treatment courses in random sequence: zopiclone or structured educational program (BBT-I) delivered in two sessions. Patients of the zopiclone-first group will receive the medication therapy for the first two weeks followed by educational program. Patients of the BBT-I-first group will receive two-week educational program followed by medication therapy.

Each treatment course will be separated by 2-weeks washout period that will provide the opportunity to evaluate the sustainability of treatment effect.

The total duration of the study will be 8 weeks with 6 visits including 1 night polysomnography (PSG), 2 face-to-face structured educational program sessions and 5 diagnostic interviews. Total duration of the study will be 2 years.

Criteria for evaluation

Primary Efficacy Endpoint

Proposed primary efficacy endpoint is change of insomnia severity index (ISI) after treatment. Criterion of response to the treatment will be defined as the reduction of ISI score reduction of >7 points from baseline. This criterion is indicative of moderate improvement and validated as clinically significant (Morin, Belleville & Belanger, 2011). Remission criterion will be defined as final

ISI score of 7 points or less. Nonresponse criterion will be defined as ISI score decrease of ≤ 7 points from baseline.

Secondary Efficacy Endpoints

1. Insomnia severity index self reported insomnia symptoms severity . Each item is scored 0 (no problem) - 4 (very big problem) with total between 0-28 (absence of insomnia (0-7); sub-threshold insomnia (8-14); moderate insomnia (15-21); and severe insomnia (22-28).
2. Beck Depression Inventory. 21-item questionnaire assessing (on 4-point Likert scales) the intensity of depressive symptoms in the past week
3. State-trait anxiety inventory. 2-part questionnaire assessing state (situational) and trait anxiety. Both situational and trait parts comprise 20 items rated on a 4-point Likert scale.
4. Dysfunctional beliefs about sleep scale. questionnaire assessing sleep related cognitions in 16 item rated on a 10-point Likert scale.

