Subjects withdrawn from the study treatment will be replaced. Subjects withdrawn from the study after Visit 5 but prior to Visit 6 won't be replaced.

Protocol Violations

Protocol violations for this study include, but are not limited to, the following:

- Failure to meet inclusion/exclusion criteria

- Use of a prohibited concomitant medication
- Non-compliance with study drug regimen, and questionnaires completion

Failure to comply with Good Clinical Practice (GCP) guidelines will also result in a protocol violation. If a protocol violation occurs, a Protocol Violation Form detailing the violation will be generated.

DATA SAFETY MONITORING

There will be no data monitoring committee

STATISTICAL METHODS AND CONSIDERATIONS

A Statistical Analysis Plan (SAP) is written describing all analyses that will be performed.

Data Sets Analyzed

All subjects matching inclusion and exclusion criteria who will complete at least one treatment course (BBT-I or medication) and fill in questionnaires prior and after the treatment will be included in the safety analysis.

Demographic and Baseline Characteristics

The following demographic variables at screening will be summarized by dose level: gender, age, height and weight. Continuous variables will be presented in means and standard deviation ($M \pm SD$).

Analysis of Primary Endpoint

Statistical significance of differences between ISI level before and after treatment for both treatment methods will be evaluated with Student's t-test after confirmation of normal variable distribution by Kolmogorov-Smirnov test. For continuous variables with distribution other than normal Mann-Whitney U-test will be used. For comparison of the proportions Pearson chi-squared test will be performed.

Criterion of response to the treatment is defined as the reduction of ISI score reduction of >7 points from baseline. This criterion is indicative of moderate improvement and validated as clinically significant (Morin, Belleville & Belanger, 2011). As well the criterion corresponds to approximately 1 standard deviation of the pretreatment values (Cohen effect size of approximately 1.0). Remission criterion is defined as final ISI score of 7 points or less. Nonresponse criterion is defined as ISI score decrease of ≤ 7 points from baseline.

Analysis of Secondary Endpoints

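### Efficacy is analysed only in patients who complete at least one course, so randomised patients who complete none are replaced and left out, and the plan has no rule for the ISI of an unfinished second course

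*Combined protocol and SAP*

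**What the plan says.** The Primary Analysis Plan in the synopsis sets the efficacy population: "Analysis of insomnia treatment will be conducted only for patients matching inclusion and exclusion criteria who will complete at least one treatment course", with questionnaires filled in before and after the treatment. Data Sets Analyzed repeats the definition but attaches it to safety: those who "fill in questionnaires prior and after the treatment will be included in the safety analysis". Analysis of Primary Endpoint names no analysis set. The efficacy restriction therefore rests on the synopsis, and no all-randomised set is defined anywhere.

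Randomisation takes place at Visit 1. Under Replacement of Subjects, "Subjects withdrawn from the study treatment will be replaced". The only exception concerns withdrawals between Visit 5 and a Visit 6 that the visit schedule does not list, so it does not reach someone who stops in the first course.

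Early Discontinuation of Study lists adverse events and non-compliance among the reasons to stop. It recommends an early discontinuation visit and encourages attendance at the remaining visits. The Early Withdrawal Visit includes completion of questionnaires.

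**The concern.** Whether a randomised patient enters the efficacy analysis depends on what happens after randomisation, and treatment can influence that. If one course loses more patients than the other, and those lost do worse than those who stay, the completer analysis flatters the course with the greater loss.

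The protocol itself gives reasons to expect unequal loss. Its Risk / Benefit Assessment states that "Brief behavioral therapy has no potential adverse effects, risks of addiction or tolerance", whereas "Zopiclone has possible hypersensitivity adverse effects as well as possible effects on central nervous system", followed by a list of effects. On that account, stops for adverse events would fall mainly on zopiclone. The Overview of Clinical Studies, however, says that cognitive-behavioural treatment, from which the brief approaches were shortened, depends on patient compliance and takes noticeable time. Stops for non-compliance could therefore fall on BBT-I.

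The second gap is one of definition. A patient who completes the first course is in the analysis, but nothing says whether an ISI taken after an unfinished second course counts. Two analysts following the plan could report different primary results.

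**Working it through.** **Who is in and who is out, on the plan's wording**

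- Completes both courses, with questionnaires: included.
- Completes the first and stops in the second: included and, if withdrawn from treatment, also replaced. Use of the second-course ISI is not stated.
- Stops in the first, stays on and completes the second: can qualify through the second course.
- Stops in the first and completes none: randomised, replaced and left out.

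**Inputs for an illustration.** The plan gives no dropout rate, target difference or SD for ISI change, so there is no stated figure to reproduce. The 40 patients and the response threshold of more than 7 points are from the plan. On that threshold it says "As well the criterion corresponds to approximately 1 standard deviation of the pretreatment values", which suggests a pretreatment SD near 7. Everything else is assumed: a completer gain of 7 on both courses, a dropout gain g of 0 or 3.5, dropout rates d1 and d2, and a within-patient correlation of 0.5.

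**Gap between the two contrasts.** The all-randomised mean gain on a course is (1 − d) × 7 + d × g. The completer contrast is 7 − 7 = 0. The gap is therefore (d1 − d2) × (7 − g), with d2 = 5%:

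| d1 | g = 0 | g = 3.5 |
|---|---|---|
| 10% | 0.05 × 7 = 0.35 | 0.175 |
| 15% | 0.10 × 7 = 0.70 | 0.35 |
| 20% | 0.15 × 7 = 1.05 | 0.525 |

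These values apply if an unfinished course is left out in either period. If the ISI of an unfinished second course is used, only first-period data are selected. With half of each course's data in each period, and stopping in the two courses unrelated, the gap halves: 0.5 × 0.70 = 0.35 at 15% against 5%.

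**Against the sampling error.** The SD of the within-patient difference is 7 × √(2 × (1 − 0.5)) = 7. With 40 pairs the SE is 7/√40 = 1.11. If only first-course stoppers are replaced and unfinished second courses are dropped, the pairs left are 20 × 0.95 + 20 × 0.85 = 36, and the SE is 7/√36 = 1.17. A gap of 0.70 is below both.

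**Patients left out.** Reaching 20 first-course completers per sequence at 15% and 5% takes 20/0.85 + 20/0.95 = 23.53 + 21.05 = 44.58 randomised, so about 4.6 are left out. This is an upper figure for these rates, because it treats every first-course stopper as completing neither course.

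**Before-after gains.** Analysis of Primary Endpoint is worded this way: "Statistical significance of differences between ISI level before and after treatment for both treatment methods will be evaluated with" a t-test. With 10% dropout on both courses and g = 0, the between-course contrast is unbiased, but each completer gain is 7 against 0.90 × 7 = 6.3 for all randomised.

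**The case against.** The rule is less severe than a strict completer analysis. A reader might infer that everyone who drops out is excluded. The documents do not support that: one completed course is enough, and a first-course stopper who stays on can qualify through the second. The group certain to be lost is those who complete neither course.

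A reader might also infer a false-positive rate above 5%. That depends on a test the plan does not name. The synopsis says "Statistical significance of differences between group for continuous variables will be evaluated with" Student's t-test, with Mann-Whitney as the alternative, and no paired test is specified. Take 15% against 5% dropout, dropouts gaining 0 and equal all-randomised means. The completer contrast is then 7 − 0.85 × 7/0.95 = 0.74, or 0.95 × 7/0.85 − 7 = 0.82. A paired test on 36 pairs with SD 7 rejects 9.4% to 10.6% of the time. An unpaired test on the same patients at correlation 0.5 rejects only about 2%. The shift in the estimate is the same either way, so the defensible point is bias in the estimate.

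A third inference, that the rule favours zopiclone, does not follow either, because the protocol gives reasons for loss on both courses.

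Finally, one might argue that ISI after stopping is already collected, so the gap is only in the analysis text. That is not explicit. The Early Withdrawal Visit lists questionnaires without naming them, the Questionnaire section ties the repeated battery with ISI to the four visits after baseline, and Appendix 1 has no early-withdrawal column and omits ISI from its questionnaire row.

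It stands that the likely bias is modest. That limits the seriousness of the point but does not remove it.

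**Conclusion.** The concern holds and should be fixed. As written, the efficacy analysis leaves out randomised patients who complete no course and replaces them, and has no rule for the ISI of an unfinished second course. Under the assumptions shown, the completer and all-randomised contrasts differ by 0.35 to 1.05 ISI points with zero gain in dropouts, and by half that with a gain of 3.5. At 15% against 5% the gap is below one standard error. Equal dropout with equal gains leaves the comparison between courses unbiased but still overstates each course's before-after gain. The direction in this trial cannot be stated in advance, and no figure in the plan is contradicted.

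**What to change.** - Make the primary efficacy set all randomised patients, analysed by assigned sequence and period.
- Use the Day 14 and Day 42 ISI for the course assigned in that period, whether or not it was finished, and the early-withdrawal ISI where the scheduled one is missing. State explicitly that ISI is among the questionnaires at the Early Withdrawal Visit.
- State one rule for a missing post-course ISI. Add a sensitivity analysis that assumes no change from a named baseline, saying whether that is Day 1 or Day 28 for the second course.
- Keep the completer analysis as a further sensitivity analysis, without claiming that the two bracket the true contrast. They need not: with completers gaining 7, dropout of 15% against 5%, and dropouts gaining 7 on the first of these courses and 0 on the other, the all-randomised contrast is 7.00 − 6.65 = +0.35, while the completer analysis gives 0 and the no-change analysis 5.95 − 6.65 = −0.70.
- Keep withdrawn patients in the analysis when a replacement is enrolled, and report withdrawals and replacements, with reasons, by course.

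The cost is text changes and a little more analysis work, with no new visits. Estimates may be less favourable and slightly less precise.

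### The objective is to compare BBT-I with zopiclone, but no estimate or confidence interval for the between-treatment ISI difference is planned

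*Combined protocol and SAP*

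**What the plan says.** The Primary Objective is comparative: "To test the effectiveness of short BBT-I program for chronic insomnia in comparison with zopiclone in Russian population". Under Primary Efficacy Endpoint, "Proposed primary efficacy endpoint is change of insomnia severity index (ISI) after treatment". Every patient is to receive both treatments in random order (Study Overview).

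The planned inference appears in two places:

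- **Analysis of Primary Endpoint:** "Statistical significance of differences between ISI level before and after treatment for both treatment methods will be evaluated with" Student's t-test, with Mann-Whitney for non-normal data. This contrast is before versus after for each method. For response and remission, "For comparison of the proportions Pearson chi-squared test will be performed".
- **Protocol Synopsis, Primary Analysis Plan:** "Statistical significance of differences between group for continuous variables will be evaluated with" Student's t-test, again with Mann-Whitney as the fallback. The groups are not defined. The type of t-test is not stated, but Mann-Whitney is a test for independent samples.

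The threshold is given as "Statistical significance will be set at a p-value less 0,05". On reporting, "Continuous variables will be presented in means and standard deviation", and categorical variables are given as percentages. The documents contain no between-treatment estimate, no confidence interval, no non-inferiority or equivalence hypothesis, and no margin.

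**The concern.** A comparative objective calls for the size of the difference between the treatments and how precisely it is known. Neither planned analysis supplies this. Two before-after tests show whether ISI fell under each method. Both can be significant when the methods differ, and one can be significant and the other not when they do not differ. The synopsis test does address a difference, but its planned output is a p-value beside two means and SDs.

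The problem shows when the comparison gives p≥0.05. That result arises when the treatments perform alike and also when they differ but the trial is too imprecise to show it. Without an interval the reader cannot tell which. Nor can the interval be rebuilt from the planned summaries, because a mean and SD per method do not give the SD of the within-patient differences. Correcting the test to a paired one, still read only against 0.05, would leave this gap.

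**Working it through.** **The plan's own figure.** N = 40 comes with no power, effect size, SD or margin (Sample Size and Randomization; Rationale for Number of Subjects), so there is no calculation to reproduce.

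**Inputs**

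- N = 40 patients, each receiving both treatments (documents).
- Significance level 0.05 (documents). Sidedness is not stated; two-sided is assumed.
- ISI SD of about 7 points. This is implied by Analysis of Primary Endpoint, which equates the 7-point criterion with about one SD of pretreatment values. Applying it to change scores is an assumption.
- Within-patient correlation ρ between the two changes is not given, so it is assumed.

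**Step 1: SD of the within-patient difference.** SD_d = SD × √(2(1 − ρ)).

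- SD 7, ρ = 0: 7 × √2 = 9.9.
- SD 7, ρ = 0.5: 7 × √1 = 7.0.
- SD 5, ρ = 0.5: 5 × √1 = 5.0.

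The range used is therefore 5 to 9.9 points.

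**Step 2: precision.** SE = SD_d/√40. The 95% CI half-width is t(0.975, 39 df) × SE, with t = 2.023. Using 38 df, to allow for a period term, leaves the half-widths unchanged to one decimal.

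**Step 3: chance of p≥0.05 when the true difference is 2 points.** This uses the noncentral t distribution with noncentrality 2/SE.

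| SD_d | SE | 95% CI half-width | 2/SE | P(p≥0.05), true difference 2 |
|---|---|---|---|---|
| 5 | 0.79 | 1.6 | 2.53 | 31% |
| 6 | 0.95 | 1.9 | 2.11 | 46% |
| 7 | 1.11 | 2.2 | 1.81 | 58% |
| 8 | 1.26 | 2.6 | 1.58 | 66% |
| 9.9 | 1.57 | 3.2 | 1.28 | 76% |

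**Step 4: what the interval adds.** Take SD_d = 7. An observed difference of 0 gives 0 ± 2.2, that is −2.2 to 2.2. An observed difference of 2 gives 2 ± 2.2, that is −0.2 to 4.2. Both have p≥0.05. The first excludes differences beyond about 2 points either way; the second is compatible with a difference of up to about 4 points. A significance statement reports them identically.

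**The case against.** The strongest reply is that the protocol never sets out to show equivalence. It asks how effective BBT-I is compared with zopiclone, which method suits a particular patient, and what predicts response. It does not say how p≥0.05 will be read, and an equivalence margin would add an objective that the sponsor did not state. This stands as far as the margin goes. It does not remove the need for an estimate with an interval, which a comparative objective requires whatever the hypothesis.

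Three stronger readings are tempting, and the documents do not support them.

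- **That the protocol expects BBT-I and zopiclone to be comparable.** Overview of Clinical Studies says "both methods have comparable effectiveness in terms of sleep quality ranging between 64"% and 88%, but it is speaking of pharmacologic and behavioral treatment as classes and of sleep quality, not of these two treatments on the ISI. The same section says there are too few BBT-I data for meta-analysis.
- **That 64% versus 88% is the contrast to power.** These are the ends of a range taken from two different sources. They are not projected ISI response rates for the two methods.
- **That the same 40 patients could establish comparability.** This depends on the margin and the SD. If the treatments are truly equal, simulation puts the chance that the 95% CI lies inside the margin, at SD_d = 7, at 74% for ±3.5 points, 51% for ±3 and 2% for ±2. At SD_d = 9.9 it is 19% for ±3.5. All these margins are illustrative. The 7-point response criterion is a within-patient cut-off, not a between-treatment margin.

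It can also be said that an interval around a biased estimate gives false comfort. The background credits behavioral treatment with lasting efficacy, and the washout is used partly to study how far effects persist, so BBT-I may carry over into the zopiclone period. The study is also open-label. These points stand as limits on how the interval is read; they apply equally to any p-value from the same data.

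**Conclusion.** The point holds as a gap in estimation and reporting: the objective is comparative, the primary-endpoint analysis is before versus after by method, the synopsis offers only a difference test at 0.05, and no between-treatment estimate or interval is planned. The 95% CI half-width of 1.6 to 3.2 ISI points, and the 31% to 76% chance of missing a true 2-point difference, rest on 40 complete patients, a two-sided 5% level and an assumed SD_d of 5 to 9.9. The 2-point difference is illustrative, not a threshold from the documents.

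The finding does not show that 40 patients are too few, or that the trial must become an equivalence trial. Nor does it say that a significant result would be uninformative: a significant between-treatment difference would count against equality.

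**What to change.** In the synopsis Primary Analysis Plan and in Analysis of Primary Endpoint:

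1. Make the main result the within-patient BBT-I minus zopiclone difference in ISI change, with each change measured from the start of its own period (Visit 1 to Visit 2, and Visit 3 to Visit 4). Give it a two-sided 95% CI from a crossover analysis that includes period and sequence. Keep the before-after results by method as description.
2. Report the paired difference in response rates with its 95% CI.
3. State that p≥0.05 alone will not be reported as equal or comparable effectiveness.
4. Say how patients who complete only one course enter the analysis, since the analysis set admits them and they supply no within-patient difference.
5. Optional: if the sponsor wishes to claim comparability, fix a margin in ISI points before any comparative data are seen, including those of the interim analysis after 20 patients. Allow the claim only if the whole interval lies inside the margin, and check first whether 40 patients suffice for that margin.

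Items 1 to 4 need a few sentences and no extra patients, visits or data; the Questionnaire section already has the ISI completed at baseline and at the next four visits. The cost is that a wide interval must be reported as inconclusive. Possible carry-over from BBT-I must also be acknowledged when the interval is read, because a two-period, two-sequence design cannot cleanly separate it from a sequence effect.
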